1.1 Transdermal drug delivery

Venepuncture causes pain and is regarded as the one of the more frequently encountered traumatic experiences among hospitalised children. The distress and fear toward needle puncture may further be aggravated in children with chronic diseases which require them to undergo regular venous cannulation or venepuncture. The pain perception in the long term may affect the psychological well-being and potentially adversely affect personal self-esteem and relationships.

Healthcare is constantly evolving as providers aim to deliver holistic care to patients. Local anaesthesia before venepuncture aligns with Good Clinical Practice and is considered a quality standard of care in children. More recently, transdermal drug delivery is rapidly evolving as a less invasive way of administering such medications in a cost-effective manner.

When it comes to transdermal drug delivery (TDD), the traditional low-cost hypodermic needles and topical creams are the most common approach to be considered. However, both have their drawbacks. For the hypodermic needle, the downsides associated include significant pain, anxiety, distress, and, worst of all, needle phobia.^{1,2} Hence, it could be challenging in children as the needle was the least favourable option among the paediatric population and the parents.^{3,4} There are also other state-of-the-art modalities to enhance transdermal delivery of local anaesthetic agents such as phonophoresis (utilising ultrasound to enhance local anaesthetic agents penetration through the skin), magnetophoresis (using magnetic field), iontophoresis (utilising electrical current to boost electrically-charged or ionic local anaesthetic agents penetration into the deeper layer of dermis) and jet injection (J-tip) (using pressurized gas to enhance subcutaneous delivery of local anaesthetic agents).⁵⁻⁸ However, the large size and the exorbitant prices of these devices warrant the utilisation of extra power sources and satisfactory training of operators before such complex devices could be handled effectively.⁹

Topical route hence appeared to be an attractive choice to be focused on. As such, topical anaesthetic creams, for example EMLA Cream (lidocaine 2.5% and prilocaine 2.5%), provide a non-invasive and convenient means of administering anaesthesia. As the drug passively diffuses across the skin, it results in a slower time of onset of effective analgesia which is around 60 minutes.^{10,11} This delayed onset of full analgesia is impractical and infeasible in a busy clinical setting. Therefore, such limitations of all available TDD methods are attributed to the human skin anatomy.

1.2 Skin structure and transdermal drug delivery

The human skin, particularly the outermost epidermal layer, is responsible for the mechanical barrier function. Unfortunately, this barrier function impedes the percutaneous entry of beneficial chemical compounds for a successful transdermal delivery of drugs.

The skin is histologically made up of 3 main layers, i.e., the outer epidermis, middle dermis, and inner hypodermis.^{12,13} For the epidermis, this avascular layer is composed of 5 keratinocytes layers and is generally 50–150 μm thick.¹² The full epidermis is constituted of the outermost *stratum corneum* (SC)

and its beneath viable epidermis (VE), with a thickness spanning from 10 to 15 μm and from 50 to 100 μm , respectively.^{13,14} In between the epidermis and dermis lies the undulating epidermal-dermal junction. The dermis is the thickest component of the skin, measuring 2 – 4 mm thick in depth.¹² The papillary and reticular dermal layers consist of active cells, connective tissues, blood vessels, lymphatics, and nerves.^{12,13} Lying underneath is the innermost hypodermis, primarily composed of subcutaneous adipose tissue as well as other histological architecture such as blood vessels, lymphatics, and nerves.¹³ Thereby, the sophisticated capillary network and nerve endings embedded in the dermis and hypodermis are substantial for systemic delivery of drugs through the transdermal route.¹² **Figure 1** illustrated the human skin structure.

[figure not shown]

Figure 1. Human skin structure. The 3 skin layers composed of i.e., epidermis, dermis and hypodermis. The structural components in each layer were illustrated in relative to its anatomical position. *Figure courtesy: Tomáš Kebert & umimeto.org - Own work, CC BY-SA 4.0*

The *stratum corneum* (SC), made up of 15 to 20 layers of dead corneocytes, is primarily responsible for the skin barrier function.¹⁴ Hence, SC is implicated for the failure in effective systemic delivery of those lipophobic and high molecular weight active pharmaceutical ingredient (API).² Nevertheless, the role of full epidermis should also be taken into account. Basement membrane and tight junctions located at the epidermal-dermal junction may confer certain resistance on molecular transportation of API across the epidermis.¹³ In the previous literature, it is also observed that drug compounds that managed to pass through the papillary dermis could subsequently reach systemic circulation and exhibit its systemic effect.¹³

The evidence was further supported by the poor bioavailability from topical preparation, whereby only 10–20% of total drug reach the circulation. In contrast, a hypodermic needle is able to penetrate the SC layer and delivers 90–100% of the loaded drug.¹ However, it punctures deep into the dermis and may hit the pain receptors.

1.3 Emergence of microneedle and its applications

With the maturation of the microfabrication manufacturing technology, research on microneedle (MN) had been carried out extensively. MN is the mimic of hypodermic needle, composed of hundreds of

micron-sized, out-of-plane protrusions, typically arranged in arrays on a patch that can be applied to the skin.^{14,15} The mechanism behind is MN creates multiple transient microchannels across the skin and disrupt the SC in a minimally invasive manner. These micron-sized conduits increase the permeability for better API transport into the systemic circulation, enhancing the therapeutic effect.

Here lie the benefits of MN whereby the needle specifications can be tailored to avoid stimulating the nociceptors and penetrating the blood vessels. The MN can be fabricated from a variety of material. Remarkably, the recent focus towards biocompatible polymer holds excellent promise over silicon or metal. Microneedle biocompatibility is the most crucial aspect to consider in the paediatric population as the skin barrier function is immature and rapidly evolving.¹² A biocompatible MN dramatically eliminates the risk of biohazard wastage and possible complications if needle breakage occurs.

Maltose, a natural carbohydrate, is preferred for its biodegradability and dissolubility within minutes.¹⁶ Its safety profile is well-recognized, which makes maltose being extensively used in pharmaceutical formulations.^{1,16} Among the MN types, coated MN refers to the solid MN coated with drugs formulation on its surface. It has a coat-and-poke feature which means the drug coating will be continuously dissolved and then released into the skin along with the polymer.²

So far, there is a paucity of prior studies investigating the effects of combined usage of microneedle and local anaesthetic application in paediatric patients requiring regular blood transfusion for their clinical conditions. There are three prior studies investigating the use of microneedle for insulin delivery and glucose monitoring in paediatric patients (children and adolescents) with type I diabetes. Gupta, Felner and Prausnitz (2011) compared the use of a single hollow microneedle as a means for intradermal delivery of insulin with the subcutaneous administration of insulin using a catheter.¹⁷ They found no significant differences in terms of insulin's area under the curve (AUC) between those two modalities but faster absorption of insulin using the former ($t_{max} = 27 \pm 13$ minutes (MN + insulin group) vs 57 ± 20 minutes (catheter + insulin group)). They also found out that pain associated with procedures was substantially lower in the MN + insulin group. However, a study by Norman et al. (2013) demonstrated higher pain scores in children and adolescents aged between 10 and 18 years old who received insulin via MN than their counterparts who received insulin subcutaneously via insulin pump.¹⁸ Nevertheless, the difference is not statistically significant. On the contrary, in a recently-published study by Samant et al. (2020) investigating the safety and suitability of different glucose monitoring modalities in 15 paediatric patients (mean age (SD): 16.8 (3.2) years) with type I diabetes, the authors demonstrated similar VAS scores between those whose glucose levels were monitored via interstitial fluid (ISF) sampling using MN patch (MN+ISF) and fingerstick capillary blood glucose monitoring.¹⁹ Interestingly, the MN+ISF group reported a statistically-significant lower VAS score mean than those who went blood glucose monitoring using intravenous catheters.¹⁹

Hence, based on these prior findings, the utilities of microneedle in alleviating pain perception associated with routine clinical procedures in paediatric patients are still inconclusive. Therefore, further investigations are obviously warranted to bridge the gap in our current understanding of microneedle utilities in paediatric patients.

1.4 The Pharmacological properties of EMLA constituents

Both constituents of EMLA cream, lidocaine and prilocaine, are amide-type local anaesthetics. They have similar pKa (7.9 (lidocaine) and 7.7-7.9 (prilocaine)), percentage of ionization at physiological pH (75-76% (lidocaine) and 67-76% (prilocaine)) and elimination half-lives ($t_{1/2} = 1.6$ hours).²⁰⁻²² However, prilocaine has a much smaller partition coefficient (129 vs 366) and percentage of protein bound (55% vs 65%) than lidocaine, resulting in a much higher volume of distribution (2.73 L/kg vs 1.30 L/kg) and a higher clearance (2.03 L/kg per hour vs 0.85 L/kg per hour) than lidocaine.^{20,22} Most

amide-type local anaesthetic agents undergo hepatic metabolism and around 5% of their mass is removed renally without metabolic transformation, except for prilocaine which could also be metabolised in the kidney.²² Hence, liver or renal impairment may affect the elimination of both agents, resulting in an elevated risk of systemic toxicity. Prilocaine results in less vasodilation than lidocaine and therefore the use of epinephrine is not warranted to lengthen its duration of action, an advantageous feature for those whom epinephrine use is contraindicated.²²

Since both lidocaine and prilocaine are less lipophilic than other local anaesthetic agents such as bupivacaine and tetracaine, they cause less cardiotoxicity. However, prilocaine causes less direct neurotoxicity (e.g. transient neurologic symptoms (TNS) and cauda equina syndrome) than lidocaine due to its larger volume of distribution, expeditious lung uptake and swift metabolism.^{20,21} Hence, prilocaine seldom reaches toxic plasma concentration level.²³ Nevertheless, prilocaine induces methaemoglobinemia formation due to its toxic metabolite, ortho-toluidine (o-toluidine).²⁴ Consequently, neonates have the highest risk of developing methaemoglobinemia since their red blood cells have insufficient methaemoglobin reductase.²² To treat this, methylene blue or ascorbic acid, could be administered intravenously to revert the ferric ion (Fe^{3+}) in the ring-like non-protein heme group of haemoglobin to its original ferrous state (Fe^{2+}).²⁵

EMLA (Eutectic Mixture of Local Anaesthetics) is a eutectic mixture of 2.5% lidocaine and 2.5% prilocaine. Due to its eutectic property, EMLA exists in an emulsified form at room temperature. Skin analgesia is induced by the diffusion of lidocaine and prilocaine transdermally, resulting in the stabilisation of neuronal membranes via the blockade of ion fluxes that are needed for action potential initiation and transmission.²⁶ EMLA should not be used on mucous membrane since it is rapidly absorbed into systemic circulation. The speed of onset, duration and depth of skin analgesia are largely reliant upon the length of application time.²⁶ Besides, the duration and onset of action are also influenced by the thickness of the skin at the application area and local blood flow.²⁷ The effects of increasing the dosage of EMLA on the onset, duration and depth of analgesia are still unknown. A maximal analgesic effect (under occlusive dressing) is achieved 2 to 3 hours post application and this may last up to 1 to 2 hours post removal.²⁶

1.5 Pain assessments

Pain is a subjective perception, rendering its assessment difficult. Several pain assessment tools had been proposed, and each presented with specific strength properties. Ideal measurement tools should always possess good sensitivity, consistency, validity, and particularly easy to understand so that they can be straightforwardly applicable to the paediatric population.^{28,29} Self-assessment scales require certain levels of comprehension skills and cognitive function. Hence, self-assessment scales are only reliable in children aged 6 years and above.²⁸ Visual Analog Scale (VAS) is considered to be the most validated tool and correlates positively with other self-measuring scales, such as Faces-pain scale revised (FPS-R) and Numerical Rating Scale (NRS). It has been further proven as an optimal tool to evaluate pain as its values can be utilised to monitor pain progression. Besides, VAS scores are also sensitive to treatment effect, and represent real difference in pain intensity at 2 different timepoints.²⁹ **Figure 2** shows a child-friendly VAS pain score device, which further gives the children a more convenient and visual way to measure pain.

[figure not shown]

Figure 2. The child-friendly VAS pain score.

Nevertheless, scientists had set eyes on the objective approach that best measures the pain intensity. With the recent help in technology advancement, a pain monitoring device had been developed based on stress induced sweating. The device relies on the firing rate of the nociceptive nerve, mirrored by the skin conductance peaks, which is then translated to the pain stimuli perceived.³⁰ The stress induced sweating is activated through skin sympathetic nerve and is independent of external environment.

[figure not shown]
1.6 Problem statements and justifications of the research

Based on our brief review of literature, there are two problem statements summarising the identified research gaps that justify the conceptual significance of this research:

- i) The combined effects of microneedle usage reduce the dose and hasten the action of EMLA Cream on skin anaesthesia in paediatric patients requiring venous cannulation for regular blood transfusion have not been properly elucidated in previous studies. This study aimed to demonstrate a better care for paediatric patients that frequently receive blood transfusion as part of the management of their clinical conditions.
- ii) The agreement between VAS score and the physiological skin conductance algesimeter index obtained using medical devices has not been previously investigated in paediatric patients. This study aimed to highlight the potential of physiological pain monitoring in critical and semi-critical care where the patient is often either semi-conscious or unconscious.

Hence, it is anticipated that our research findings may satisfactorily provide the answers to the problem statements above, resulting in significant application of microneedle in TDS of drugs such as EMLA Cream, and the use of physiological monitoring of pain in paediatric patients. The conceptual framework (**Figure 3**) diagrammatically summarizes our research underpinnings, postulates and justifications.

1.7 Conceptual framework

CHAPTER II

STUDY OBJECTIVES

2.1 General Objective

To evaluate if the pain scores are different during venous cannulation through a pre-anaesthetized skin patch, with and without the use of microneedle.

2.2 Specific Objectives

- 2.2.1 To compare Visual Analogue Scale pain scores among Microneedle with 1 Finger Tip Unit EMLA Cream (experimental group) applied for 30 minutes, Microneedle with 0.5 Finger Tip Unit EMLA (experimental group) applied for 30 minutes, Microneedle with 1 Finger Tip Units EMLA applied for 15 minutes, and 1 Finger Tip Units EMLA Cream only applied for 30 minutes (controls) groups.
- 2.2.2 To compare skin conductance algesimeter index among Microneedle with 1 Finger Tip Units EMLA Cream (experimental group) applied for 30 minutes, Microneedle with 0.5 Finger Tip Unit EMLA (experimental group) applied for 30 minutes, Microneedle with 1 Finger Tip Units EMLA applied for 15 minutes, and 1 Finger Tip Units EMLA Cream only applied for 30 minutes (controls) groups.
- 2.2.3 To evaluate the agreement between the Visual Analogue Scale pain scores obtained and the skin conductance algesimeter index obtained via PainMonitor™ machine

2.3 Research Questions

- 2.3.1 Is there any difference in terms of VAS pain score means among the MN with 1 Finger Tip Unit (FTU) EMLA Cream (30-minute application), MN with 0.5 FTU EMLA (30-minute application), MN with 1FTU EMLA cream (15-minute application), and 1 FTU EMLA Cream only (30-minute application, controls) groups?
- 2.3.2 Is there any difference in terms of skin conductance algesimeter index means among the MN with 1 FTU EMLA Cream (30-minute application), MN with 0.5 FTU EMLA (30-minute application), MN with 1FTU EMLA cream (15-minute application), and 1 FTU EMLA Cream only (30-minute application, controls) groups?
- 2.3.3 Is there any agreement between the VAS pain score and the skin conductance algesimeter index obtained via PainMonitor™ machine?

2.4 Research Hypotheses

- 2.4.1 There is at least a difference in terms of the VAS pain score means among the MN-with-1-FTU-EMLA (30-minute application time), MN-with-1FTU-EMLA (15-minute application time), MN-with-0.5 FTU-EMLA (30-minute application time), and 1-FTU-EMLA-only (30-minute application time) groups.
- 2.4.2 There is at least a difference in terms of the skin conductance algesimeter index means among the MN-with-1-FTU-EMLA (30-minute application time), MN-with-1FTU-EMLA (15-minute application time), MN-with-0.5-FTU-EMLA (30-minute application time), and 1-FTU-EMLA-only (30-minute application time) groups.
- 2.4.3 There is agreement between the VAS pain score and the skin conductance algesimeter index obtained via PainMonitorTM machine.

CHAPTER III

RESEARCH METHODOLOGY

3.1 Research Design

This is a prospective, phase II, single-centre, single-blind, cross-over, randomized negative-controlled (without microneedle (MN)) trial at Hospital Canselor Tuanku Muhriz (HCTM), Universiti Kebangsaan Malaysia. Eligible participants will be randomized in a cross-over fashion to one of 24 treatment sequences as shown in **Figure 4**.

This crossover design is chosen over the more conventional parallel-group randomized trial since the lesser intra-patient variability than the inter-patient variability, thus minimising the required sample size. The study investigators also do not anticipate the inherent disadvantages associated with this trial design (greater attrition rate, prolonged carry-over effects and the inconsistency of participant's condition) will be present in this study.

3.2 Time period/ Duration

From August 2021 until August 2022 (52 weeks).

3.3 Study site

Paediatric day-care centre at level 4 of UKM Medical Centre.

3.4 Study population and sampling method

Thalassaemic patients who came for regular blood transfusion at HCTM who fulfil the inclusion and exclusion criteria and voluntarily provide the voluntary written informed consent. Convenient sampling will be used to obtain the study subjects to prevent insufficient recruitment caused by the paucity of eligible study participants.

3.5 Inclusion Criteria

- i) Patient aged at least six years to below eighteen years old
- ii) Patients requiring venous cannulation for blood transfusion

3.6 Exclusion Criteria

- i) Patient with a previous history of sensitization or allergy to EMLA Cream
- ii) Patient with a previous history of allergy to materials used in the study i.e., plaster, electrodes, maltose, Polyvinyl Alcohol (PVA), and Polyethylene Terephthalate (PET)
- ii) Patient exposed to analgesic usage within 24 hours prior to the procedure
- iii) Generalized skin disorder/ rash
- iii) Agitated/ fretful patient

3.7 Ethical issues

Voluntary written informed consent will be obtained from each study participant. This study will be conducted in accordance to the principles of ethics in human research laid as stipulated by the Declaration of Helsinki (18th World Medical Association General Assembly, 1964) and the Good Clinical Practice (GCP) guidelines.³¹ Ethical approval will be obtained from the UKM Research Ethics Committee (Human) (JEPUKM).

To aid the transparency of reporting, the trial will be registered at the Clinical Trials.gov registry (<https://clinicaltrials.gov/>). The full trial protocol will be made available in the same trial registry and prepared according to the Consolidated Standards of Reporting Trials (CONSORT) guideline for crossover design and the 2013 Standard Protocol Items: Recommendations for Interventional Trials (SPIRIT) statement.^{32,33} The trial data with study participant identification numbers removed (Hospital RN, Identity Card (IC) numbers, subject's identification number (SIDNO) will be made available to the public via Harvard Dataverse repository for research data (<https://dataverse.harvard.edu>) to ensure the transparent dissemination of study findings and fulfil the requirements for the future publication of the findings of this research.

3.8 Randomization procedure

For random allocation, simple randomization with random allocation rule (RAR) will be used by which a list of random numbers will be generated in a balanced 1:1 ratio (based on 24 different treatment sequences) using the randomizeR package version 20.0 executed on R platform.³⁴ The list of generated random numbers will be used to allocate the study participants to either intervention or control branch. The allocation sequence generated will be kept in a password-protected document that is only accessible to the statistician to maintain allocation concealment. To further guarantee allocation concealment is satisfactory, randomisation code will not be revealed until the participants have been definitively recruited into the trial, which is after all baseline measurements are made and all eligibility criteria are deemed fulfilled. Besides, allocation concealment is further assured by ensuring the information on the intervention allocation is only given to the person who will be administering the allocation via secured phone calls (central randomization). Consecutive recruitments will be made until the final intended sample size is reached.

For this study, the study participants, outcome assessors, care providers and data handlers will be blinded to the study interventions. Only the statistician and the person who will be administering the interventions will be unblinded to the study interventions. Besides, unique code to indicate each treatment sequence assignment will be utilised to ensure that the unintentional / intentional unblinding of one trial participant will not compromise the integrity of blinding for the rest of study participants. The main unblinded trial persons (the statistician and the key person who will be administering the intervention) are instructed not to divulge the identity of the allotted treatments to other blinded trial persons. The success of blinding will be determined by asking the blinded trial persons (e.g. study participants, care providers, outcome assessors) to guess the interventions received and then compare the results obtained with what would be anticipated by chance. Blinding indices such as James' Blinding Index or Bang's blinding Index could also be computed to objectively evaluate the success of blinding.^{35,36}

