3.12 Sample size calculation

The determination of sample size is carried out using G*Power software, version 3.1.9.6 (Universitat Kiel, Germany; February 2020) using the F-test family, Repeated Measure (RM) ANOVA within and within-between interaction sub-options. The type I error (α) and the study power ($1 - \beta$, where β = type II error) are fixed at 0.05 and 0.80, respectively.

Due to scarcity of information from previous literature on paediatric population, we could not use the parameter estimates (standard deviation of the differences, mean differences between pairs) from prior studies as guides for our sample size calculation. However, to circumvent this, we utilise Cohen's guideline on choosing the effect size for this study.⁴⁴ We assumed that the Cohen's d is large ($d = 0.8$) and used this as our effect size. It had been demonstrated by a

previous study on the efficacy of microneedle as a delivery method for 5% lidocaine dental gel (Septodont, UK) that the effect size could be that large, thus justifying our choice of effect size in general.⁴⁵ For objectives 1 and 2, we used the RM-ANOVA within-group comparison sub-option and fix the number of groups and measurements to 1 and 4, respectively. Based on prior guidelines, moderate-to-high correlations between the within-group measurements ($r = 0.7$) are assumed.^{46,47} For non-sphericity correction (ϵ), a value of 0.75 is assumed since the sphericity assumption is rarely fulfilled in practical and actual trial setting due to unequal correlations between measurement pairs and the chosen ϵ value is midway between its lower bound of 0.5 and maximal value of 1 to fairly preserve the RM-ANOVA test against inflated type I error rate (α) when non-sphericity occurs.⁴⁸⁻⁵¹ Hence, for objectives 1 and 2, we require a sample size of 23 subjects. Assuming a 10% attrition (drop-out) rate, the total sample size is 26 ($n_{\text{total}} = 26$).

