For objective 2, we could not calculate the sample size since we don't have the estimate of the standard deviation of the differences (denoted by (s) henceforth) between the two methods for pain evaluation (the VAS score and the skin conductance algesimeter index obtained via PainMonitor™). Information on (s) is required since the sample size formula for evaluating limit of agreement require s parameters to be explicitly specified. However, we could roughly assess the precision of the limit of agreements (as per (s) magnitude) based on the sample size proposed for objective 1 and 2 using the formula recommended by the original authors.⁵² Based on Bland and Altman (1986), the 95% CI of limit of agreement is given by:

$$\pm 1.96 * \sqrt{3/n} * s^{52},$$

where s = standard deviation of the differences between VAS score and the skin conductance algesimeter index. If we assume a sample size of 24, then the precision of the limit of agreement is:

$$\pm 1.96 * \sqrt{3/26} * s = \pm 0.67 * s,$$

which we deem a satisfactory precision in our case.

However, due to absence of an estimate of (s) from prior studies, the actual precision could not be accurately estimated, thus highlighting the importance of (s) in the actual sample size calculation. Thus, it is hoped the estimate of (s) obtained from this study will be used as a guide for calculating a sample size for a future follow-up study that can answer this study objective more reliably. However,

Hence, the biggest overall sample size required for this study is 26 ($n_{\text{total}} = 26$).

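### Section 3.8 promises a 1:1 allocation over 24 sequences that 26 children cannot give and names two incompatible methods; even under the balanced method, the planned carryover test is uninformative

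*Combined protocol and SAP*

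**What the plan says.** Section 3.1 states that "Eligible participants will be randomized in a cross-over fashion to one of 24 treatment sequences", and Table 1 in section 3.15 lists all 24 orders of the four treatments. Every child is meant to receive all four.

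Section 3.8 gives the method: "simple randomization with random allocation rule (RAR) will be used", and "random numbers will be generated in a balanced 1:1 ratio (based on 24 different treatment sequences". The next sentence says that the list is "used to allocate the study participants to either intervention or control branch". No list length, block size or rule for children beyond the first 24 is given.

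On numbers, section 3.12 says "we require a sample size of 23 subjects" and "Assuming a 10% attrition (drop-out) rate, the total sample size is 26", and concludes that "the biggest overall sample size required for this study is 26".

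On analysis, section 3.14 plans a repeated-measures ANOVA, described without a visit term, and a mixed model fitted both with and without period effects. Neither is named as primary. Carryover is to be judged from the interaction of treatment with sequence in the ANOVA.

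**The concern.** Three statements in section 3.8 do not fit together. A 1:1 ratio over 24 sequences needs a multiple of 24 children. Simple randomisation draws each child independently and fixes no totals, whereas RAR fixes them in advance. Allocation to an intervention or a control branch describes a two-arm parallel trial. A statistician could not build one definite list from this text.

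Two things are at stake. One is the balance of treatments over visits, which protects the comparison from visit effects such as growing familiarity with the procedure. It matters most in an analysis without a visit term. The other is whether the data can say anything about carryover when there is about one child per sequence.

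**Working it through.** **Inputs.** 24 sequences (section 3.1, Table 1); 23 evaluable and 26 in total with 10% attrition (section 3.12); 4 visits. The 23 is taken as stated.

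**The plan's own figure.** 23/(1 − 0.10) = 25.6, rounded up to 26. This reproduces.

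**Equal allocation.** 26/24 = 1.08. The nearest split is 22 sequences used once and 2 used twice. With 23 completers at least one sequence is empty under any scheme. Exactly 24 children would allow equality, but 24 × 0.9 = 21.6 evaluable falls below 23.

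**Empty sequences.**
- Simple randomisation: 24 × (23/24)^26 = 7.9 (SD 1.55).
- RAR on a list of 48 stopped at 26: 24 × (22 × 21)/(48 × 47) = 4.9.
- RAR on a list of 26: 0.
- RAR on a list of 26 less 3 children at random: 22 × 3/26 + 2 × 24/2600 = 2.6, where 2600 is the number of ways to lose 3 of 26.

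**Balance and precision.** Let T be the visit-by-treatment count matrix for n children. The information on treatments after removing child and visit effects is nI − T′T/n. Efficiency is 2/n divided by the mean variance of a treatment contrast. The simple and RAR rows come from 10,000 simulated lists each. Efficiencies in the Williams rows, and the counts after losses, come from 1,500 lists each. Between-child residual df are children minus filled sequences.

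| Scheme | Mean minimum / maximum arm-by-visit count | Mean efficiency | Between-child df |
|---|---|---|---|
| Simple, 26 | 2.8 / 10.6 | 96.0% | 26 − 16.1 = 9.9 |
| RAR, list of 48 stopped at 26 | 3.8 / 9.1 | 98.2% | 26 − 19.1 = 6.9 |
| RAR, list of 26 | 6.0 / 7.6 | 99.7% | 26 − 24 = 2 |
| RAR, list of 26, less 3 | 4.2 / 7.2 | 99.2% | 23 − 21.4 = 1.6 |
| Williams square in fours, 26 | 6 / 7 | 99.8% | 26 − 4 = 22 |
| Williams square in fours, less 3 | 4.7 / 6.7 | 99.3% | 23 − 4 = 19 |

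For RAR on 26, all 276 ways of placing the two extra children were enumerated: every count is 6 to 8 and efficiency is 99.6 to 99.8%.

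**Analysis without a visit term.** For two treatments in one child, the mean squared difference in visit position is (1+1+1+4+4+9)/6 = 3.33. Over 26 independent children the mean difference has SD √(3.33/26) = 0.36 visits. Under RAR on 26 the first 24 cancel, and the two extras give √(2 × 3.33 × 22/23)/26 = 0.10 visits. The documents give no visit trend. Assuming a linear trend of 2, 5 or 10 mm VAS per visit, the SD of the noise added to a contrast is 0.7, 1.8 or 3.6 mm under simple randomisation, and 0.2, 0.5 or 1.0 mm under RAR.

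**Carryover test under RAR on 26.** The 26 × 3 = 78 within-child df split into 3 for treatment, 23 × 3 = 69 for the interaction and 2 × 3 = 6 for error. After 3 random losses no residual df remain if the losses break both duplicated pairs: (4 × 22 + 4)/2600 = 3.5% of cases. With a Williams square the split is 3, 9 and 66.

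**The example square.** ABDC, BCAD, CDBA and DACB are all in Table 1. Each treatment occurs once at each visit, and each of the 12 ordered pairs of successive treatments occurs once.

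**The case against.** A reader might infer that about 8 sequences will be empty and that the arms will be unbalanced over visits. The documents do not support that. The sentence that says simple also names RAR and a balanced ratio, and balance fits RAR only. On a list of 26, RAR leaves no sequence empty and keeps every count within 6 to 8. Arm totals are equal by design under any list, because each child is to receive all four treatments. Even pure simple randomisation costs only about 4% in efficiency if visit is modelled, and chance imbalance adds variance, not systematic bias. All of this stands.

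The Williams square also has limits. Its precision gain over RAR is negligible, 26 is not a multiple of four, and a fixed square in blocks of four lets the unblinded administrator deduce the last sequence of each block. These stand as costs.

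Finally, drug carryover looks unlikely on the protocol's own figures: a washout of at least 3 weeks against elimination half-lives of 1.6 hours. That bears on whether carryover exists. It does not rescue a test that the plan relies on and that cannot detect it.

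**Conclusion.** The stated 1:1 allocation over 24 sequences is unattainable with 26 children, and the method cannot be reproduced from the text. How much this affects visit balance depends on which half of the sentence is carried out: about 96% efficiency and counts of about 3 to 10 under simple randomisation, or about 99.7% and counts of 6 to 8 under RAR on 26. A RAR list of 48 stopped at 26 lies between. The RAR reading is the more natural one, so visit imbalance is a risk of the wording only.

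The firmer consequence belongs to that same reading. With all 24 sequences filled, the carryover test has 2 between-child df (6 within-child). After three losses the mean is about 1.6, and in about 3.5% of cases none remain. A non-significant result would say nothing. Simple randomisation leaves more df, but only because fewer sequences are used.

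Assumptions: the three losses are at random and those children are left out of the ANOVA entirely; the millimetre figures rest on an assumed visit trend.

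**What to change.** In section 3.8, delete the reference to simple randomisation, the 1:1 claim over 24 sequences and the wording about intervention and control branches. State that children are randomised in permuted blocks to the four sequences of a Williams square from Table 1, for example ABDC, BCAD, CDBA and DACB. State the list length and block sizes. Say that at 26 the last block is incomplete, so that with blocks of four the counts are 6 to 7 per arm per visit; exact balance needs 24 or 28. Align section 3.1, section 3.9.2, Table 1 and Figure 4.

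In section 3.14, put visit in the primary model. This also matters for the carryover test: in a four-sequence square, 3 of the 9 interaction df are the visit effect, so without a visit term the test mixes the two.

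The cost is a new list and edited text, with no extra patients. Do not expect better precision: the gain over a correctly run RAR is about 0.1 percentage point. The gain is in the carryover test, with 22 between-child df (19 after three losses). Predictability to the unblinded administrator is reduced by larger or varied blocks in multiples of four under the central allocation already planned. The price is a slightly wider spread if the last incomplete block is a large one.
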